	
categories for safety assessments given in the previous SAP version in different subsections
 
 4. Section "10.7.3.2 Adverse events" added with definition of an AE and rules for reporting AEs 5. Section "10.7.3.3 Treatment-emergent adverse events" added with information from the previous SAP version and additional details 6. Addition of subsections "10.7.3.4 Adverse events of special interest" "10.7.3.5 Relationship to study drug" "10.7.3.6 coding of adverse events" "10.7.3.7 Grading of adverse events" "10.7.3.8 Deaths" "10.7.3.9 General rule for reporting" 7. Section "10.7.3.10 AE summaries" contains variables to be summarized from the previous SAP version with additional variables to be summarized 	
overview
 
 4. Section added for more details 5. Information on TEAE expanded. Additional details are provided 6. Subsections added 7. List of variables to be summarized expanded. Additional variables are provided with additional details
10.8 Secondary objective 8	
 1. Section "9.4.2 Immunogenictiy analysis" from the previous SAP version renamed to "10.8 Secondary objective 8" with addition of subsections 2. Addition of the categorization of anti-MOR00208 antibody response 3. Addition of the subsections "10.8.1 Objective" "10.8.2 Endpoint: Percentage of patients who develop anti-MOR00208 antibodies as determined by a positive anti-MOR00208 antibody titre" "10.8.3 Main analysis" 	
 1. New structure provides a better overview of the endpoint 2. The categorization added 3. Information and details from the previous SAP version remained unchanged
10.9 Secondary objective 9	
 1. Section "9.4.1 Pharmacokinetic Analysis" from the previous SAP version renamed to "10.9 Secondary objective 9" with addition of subsections 2. Addition of information on population PK analysis in subsection "10.9.3.3 Population PK analysis" 	
 1. New structure provides a better overview of the endpoint. Information in the previous SAP remained unchanged with minor wording corrections 2. Section added for more details
10.10 Secondary objective 10	Section with corresponding subsections and details added	Section added for more details
10.11 Secondary objective 11	Section added with reference to section 10.5.3.2	Section added for more details
10.12 Secondary objective 12	
 1. Section "9.4.3 Exploratory Biomarker Analysis" from the previous SAP version renamed to "10.11 Secondary objective 11" with addition of subsections 2. Addition of subsections "10.12.1 Objective" 	
 1. New structure provides a better overview of the endpoint. 2. Information on the subgroups expanded. Additional details are provided

STATISTICAL ANALYSIS PLAN

 MorphoSys AG
 MOR208C203

	"10.12.2 Endpoint" "10.12.3 Main analysis" "10.12.4 Sensitivity analyses" with detailed description of subgroups, including new subgroups	
11 Exploratory efficacy analyses	Section added with minor information on "time to response" from the previous SAP version	Section added for more details
12 Descriptive biomarker analyses	Section added	Section added for more details
13 Additional Safety analyses	
 1. Section "9.5.3 Vital Signs; body Weight and Height" from the previous SAP version renamed to "13.2.1 Vital signs variables" with minor changes in wording and additional variables 2. Addition of subsection "13.2.2 Vital signs analysis" with details 3. Section "9.5.2 Physical examination" from the previous SAP version renamed to "13.3 Physical examination" with some wording and editorial changes 4. Section "9.5.4 Electrocardiograms (12-lead ECG)" from previous SAP renamed to "13.4 Electrocardiogram (ECG)" 5. Section "13.4.1 ECG Variables" added 6. Section "13.4.2 ECG Analysis" added with information on normal ranges for ECG variables from section "9.5.4 Electrocardiograms (12-lead ECG)" from previous SAP version and additional details on analyses with detailed table on clinically notable ECG values 7. Section "9.5.5 Clinical Laboratory Evaluations" from previous SAP version renamed to "13.5 Laboratory data" 8. Section "13.5.1 Laboratory Variables" added with less laboratory parameters 9. Section "13.5.2 Grading of Laboratory data" added 10. Section "13.5.3 Laboratory Analysis" added 11. Section "13.6 ECOG scores analyses" added 12. Section "13.7 B-symptoms" added 	
 1. Some variables added 2. Information added 3. Information from the previous SAP version remained unchanged with minor wording changes 4. New structure and numbering of section provides a better overview 5. Section added for more details 6. Information from previous SAP remains unchanged. Additional details provided, including table on clinically notable ECG values 7. New structure and numbering of section provides a better overview 8. Not all laboratory variables need to be analysed 9. Section added for more details 10. Section added for more details 11. Information on ECOG expanded, additional information is provided 12. Section added for more details
14 General Guidance on reporting	Section added	To provide a consistent reporting
15 Reference	Standard Operating Procedure from ██████████ removed	Not needed due to change of CRO

2. LIST OF ABBREVIATIONS AND DEFINITION OF TERMS

ABC	Activated B-cell
ADCC	Antibody-dependent cell-mediated cytotoxicity
ADCP	Antibody-dependent cell-mediated phagocytosis
ASCT	Autologous stem-cell transplantation
AE	Adverse event
ANOVA	Analysis of variance
ATC	Anatomical therapeutic chemical
BCL-2/-6	B-cell CLL/lymphoma 2/6
BLQ	Below the limit of quantification
BMI	Body mass index
CD16/19/20	Cluster of differentiation 16/19/20
CHOP	Cyclophosphamide, doxorubicin, vincristine, and prednisone
CLL	Chronic lymphocytic leukaemia
CR	Complete response
CRF	Case report form
CRS	Cytokine release syndrome
CSR	Clinical study report
CT	Computed tomography
CTC(AE)	Common Terminology Criteria (for Adverse Events)
CV	Coefficient of variation
DCR	Disease control rate
DLBCL	Diffuse large B-cell lymphoma
DoR	Duration of response
ECG	Electrocardiogram
ECOG	Eastern Cooperative Oncology Group
eCRF	Electronic case report form
EMA	European medicines agency

STATISTICAL ANALYSIS PLAN

MorphoSys AG

MOR208C203

EOT	End of treatment
FAS	Full analysis set
FDA	Food and Drug Administration
FU	Follow up
GCB	Germinal center B -cell
GEP	Gene expression profiling
HDC/HDT	High-dose chemotherapy
HR	Heart rate
IAS	Immunogenicity analysis set
ICF	Informed consent form
ICH	International Conference on Harmonization
IHC	Immuno-histochemistry
IND	Investigational new drug
INV	Investigator
IPI	International prognostic index
IRR	Infusion-related reaction
IRC	Independent Radiology/Clinical Review Committee
IV	Intravenous
IWG	International Working Group
LEN	Lenalidomide
mAb	Monoclonal antibody
MedDRA	Medical Dictionary for Regulatory Activities
MRI	Magnetic resonance imaging
ms	Millisecond
NCI	National Cancer Institute
NCS	Not clinically significant
NHL	Non-Hodgkin lymphoma
NK	Natural killer

STATISTICAL ANALYSIS PLAN

 MorphoSys AG
 MOR208C203

ORR	Objective response rate (complete response + partial response)
OS	Overall survival
PD	Progressive disease
PE	Physical examination
PET	Positron emission tomography
PFS	Progression-free survival
PK	Pharmacokinetics
PKAS	PK analysis set
PPS	Per-protocol set
PR	Partial response
PR (ECG)	PR interval
PT	Preferred term
QC/QA	Quality control/quality assurance
QRS	QRS interval
QT	QT interval
QTc	QT interval corrected
QTcB	QT interval, Bazett's correction
QTcF	QT interval, Fridericia's correction
R-CHOP	R ituximab plus c yclophosphamide, h ydroxydaunorubicin (also referred to as doxorubicin or adriamycin), and o ncovin (vincristine) plus p rednisone or p rednisolone
RR (ECG)	Relative rate
R-R DLBCL	Relapsed or refractory diffuse large B-cell lymphoma
R-R NHL	Relapsed or refractory non-Hodgkin lymphoma
R-R CLL/SLL	Relapsed or refractory chronic lymphocytic leukaemia/ small lymphocytic lymphoma
RTX	Rituximab
SAE	Serious adverse event
SAF	Safety analysis set

**STATISTICAL ANALYSIS PLAN**

MorphoSys AG

MOR208C203

SAP	Statistical analysis plan
SD	Stable disease
SI	System international
SLL	Small lymphocytic lymphoma
SmPC	Summary of product characteristics
SOC	System Organ Class
SOP	Standard Operating Procedure
SPM	Second primary malignancy
StD	Standard deviation
TEAE	Treatment-emergent adverse event
TFR	Tumour flare
TLS	Tumour lysis syndrome
TTNT	Time to next treatment
TTP	Time to progression
US	United States
WHO-DDE	World Health Organization–Drug Dictionary Enhanced

3. INTRODUCTION

This Statistical Analysis Plan (SAP) describes the planned analysis and reporting of data collected from MorphoSys protocol MOR208C203, Amendment 3.0, Version 6.0, dated 23-Oct-2017. Any amendments to the protocol which do not affect the statistical aspects of the trial will not necessitate an SAP update.

This study is a single-arm, multicentre, open-label, phase IIa study of lenalidomide (LEN) combined with MOR00208 in adult patients with relapsed or refractory diffuse large B-cell lymphoma (R-R DLBCL). The structure and content of this SAP provides sufficient detail to meet the requirements identified by the Food and Drug Administration (FDA), European Medicines Agency (EMA), and International Conference on Harmonization (ICH) of Technical Requirements for Registration of Pharmaceuticals for Human Use: Guidance on Statistical Principles in Clinical Trials. All work planned and reported from this SAP will follow internationally accepted guidelines, published by the American Statistical Association and the Royal Statistical Society, for statistical practice.

The planned analyses identified in this SAP may be included in clinical study report (CSRs) and/or in relevant summary report documents (e.g. regulatory submissions, or future manuscripts). Also, *post-hoc* exploratory analyses not necessarily identified in this SAP may be performed to further examine study data and will not require updating the final SAP. Any post-hoc, or unplanned, exploratory analysis performed will be clearly identified as such and described in the final CSR.

The following documents were reviewed in preparation of this SAP:

- Clinical Research Protocol MOR208C203, Amendment 3; Version 6.0, dated 23-Oct-2017
- Annotated electronic Case report forms (eCRFs), Version 6.0, dated 03-May-2018
- ICH Guidance on Statistical Principles for Clinical Trials (E9)

The reader of this SAP is encouraged to also read the clinical protocol, and other identified documents, for details on the planned conduct of this study. Operational aspects related to collection and timing of planned clinical assessments are not repeated in this SAP unless relevant to the planned analysis.

4. STUDY OBJECTIVES AND ENDPOINTS

An overview of the study objectives and endpoints is depicted in Table 1.

Table 1: Study objectives and endpoints

Study objective	Endpoint	Analysis
Primary objective:	Primary endpoint:	
To determine the activity of a combination of LEN with MOR00208 in terms of objective response rate (ORR = complete response (CR) + partial response (PR)) in adult patients with R-R DLBCL	Best Objective Response Rate (ORR), defined as the proportion of responders whose best response at any time throughout treatment or follow-up is complete or partial (ORR=CR+PR)	See section 9
Secondary objectives:	Secondary endpoints:	
1. To determine the disease control rate (DCR = CR + PR + stable disease (SD) as best response)	Disease Control Rate (DCR = CR+PR+SD as best response)	See section 10.1
2. To determine progression-free survival (PFS)	Progression-free Survival (PFS)	See section 10.2
3. To determine the duration of response (DoR)	Duration of Response (DoR)	See section 10.3
4. To determine the overall survival (OS)	Overall Survival (OS)	See section 10.4
5. To determine time to progression (TTP)	TTP	See section 10.5

STATISTICAL ANALYSIS PLAN

 MorphoSys AG
 MOR208C203

6. To determine the time to next treatment (TTNT)	To determine the time to next treatment (TTNT)	See section 10.6
7. To determine the safety of LEN combined with MOR00208 assessed according to the frequency and severity of adverse events (AEs)	Incidence, frequency and severity of treatment-emergent AEs	See section 10.7
8. To assess the potential immunogenicity of MOR00208 (anti-MOR00208 antibodies)	Anti-MOR00208 antibody formation (ADA): number and percentage of patients who develop anti-MOR00208 antibodies; Titer determination; Characterization of ADA-positive samples (neutralizing vs non-neutralizing)	See section 10.8
9. To assess the pharmacokinetics (PK) of MOR00208	Summary statistics for PK: plasma concentration-time profiles of MOR00208 and appropriate individual PK parameters (e.g. accumulation ratios).	See section 10.9
10. To make a preliminary evaluation of ORR, DCR, DoR, PFS, OS, TTP and TTNT in patients treated with a combination of LEN plus MOR00208 in cohorts with a “low risk”, “low-intermediate risk”, “high-intermediate risk” and “high risk” according to the International Prognostic Index (IPI)	
ORR, DCR, DoR, PFS, OS, TTP, and TTNT stratified by:
 
 four risk categories: “low risk”, “low-intermediate risk”, “high-intermediate risk” and “high risk” 2 risk categories: patients with “low risk” and “low-intermediate risk” vs. patients with “high-intermediate risk” and “high” risk 	See section 10.10
11. To compare each patient’s TTP on LEN plus MOR00208 with the TTP of their most recent prior therapy	TTP in patients treated with LEN plus MOR00208, and TTP in each individual’s most recent prior treatment therapy.	See section 10.11
12. To correlate efficacy parameters with certain	Stratification of efficacy parameter according	See section

STATISTICAL ANALYSIS PLAN

 MorphoSys AG
 MOR208C203

biomarkers (e.g. baseline tumour CD19 expression level, peripheral Natural Killer (NK) cell count, constitutional FcγRIIIa and FcγRIIa polymorphism status)	to the following subgroups: 
 • FcγRIIIa affinity (high affinity: FCGR3A-158V homozygosity vs. low affinity: FCGR3A-158F homozygosity, or FCGR3A-158F/V heterozygosity) • FcγRIIa affinity (high affinity: FCGR2A-131H homozygosity vs. low affinity: FCGR2A-131R homozygosity, or FCGR2A-131H/R heterozygosity) • Cell-of-origin (determined by immunohistochemistry/central pathology: Germinal center B-cell (GCB) vs. non- GCB) • Peripheral NK cell numbers at baseline (< median of NK cell numbers/μl vs. ≥ median of NK cell numbers/μl) 	10.12
---	--	-------

5. STUDY DESIGN

5.1 General study design

This is a single-arm, multicentre, open-label phase II, study of LEN combined with MOR00208 in adult patients with DLBCL who have relapsed after or are refractory to at least one, but no more than three previous systemic regimens administered for the treatment of their DLBCL and who are not candidates for high-dose chemotherapy (HDC) and subsequent autologous stem cell transplantation (ASCT) and are thus considered to have exhausted their therapeutic options for demonstrable clinical benefit. One prior therapy line must include an anti-CD20 targeted therapy (e.g. rituximab (RTX)).

Patients with primary refractory DLBCL, patients with known "double/triple hit" DLBCL genetics or those who have undergone previous allogenic stem cell transplantation are not eligible for study participation. Additionally, patients with a history of ASCT ≤3 months prior to the requirement to provide signed informed consent cannot be included in the study.

This study will consist of two parts, which will be performed sequentially. During the course of the first part, six patients will be enrolled in the study and will complete the first cycle of study treatment. Once the sixth patient in the cohort has completed Cycle 1 Day 22 visit, a Safety Review Panel which consists of the sponsor, a representative of the participating investigators and two independent expert clinical haematologists will perform a clinical safety review based on the number and type of AEs occurring during the first cycle and on laboratory values (biochemistry and haematology). A LEN dose will be considered tolerated

**STATISTICAL ANALYSIS PLAN**MorphoSys AG
MOR208C203

or in need of reduction after discussion of these data between the sponsor's Clinical Program Leader (or designee), the sponsor's Drug Safety Officer (or designee), a representative of the participating investigators and two expert clinical haematologists who are not participating in the study. The second part of the study will only be opened for enrolment by the sponsor following the outcome of this discussion.

Treatment consisting of **LEN** and **MOR00208 combination** will be administered up to twelve 28-day cycles (Figure 1) at specified dose levels.

MOR00208 dose: 12 mg/kg

[figure not shown]
For the first three cycles (Cycles 1-3) of the study each cycle will consist of a MOR00208 infusion on Day 1, Day 8, Day 15 and Day 22 of the cycle. Additionally, a loading dose will be administered on Day 4 of Cycle 1. Thereafter MOR00208 will be administered on a bi-weekly (every 14 days) basis with infusions on Day 1 and Day 15 of each 28-day cycle.

MOR00208 can be administered until disease progression, or unacceptable toxicity, or discontinuation for any other reason, whichever comes first. It is up to the investigator to decide according to the individual risk/benefit ratio if the patient should continue further treatment with MOR00208 in spite of disease progression.

LEN:

Patients will self-administer a starting dose of 25 mg oral LEN daily on Days 1–21 of each cycle. Treatment with LEN may be modified in a de-escalating fashion or discontinued based upon clinical and laboratory findings. Detailed dose modification guidelines to manage haematologic and/or other toxicities are provided in the respective sections of the protocol. LEN can be given for up to 12 cycles in total. Treatment with LEN will have to be stopped in the case of disease progression, or unacceptable toxicity, or discontinuation for any other reason, whichever comes first.

Figure 1: Study design

Abbreviations: EOT=end of treatment; FU=follow-up; LEN=lenalidomide; R-R DLBCL=relapsed or refractory diffuse large B-cell lymphoma.

Objective disease response assessments will be made according to the revised response criteria based on the guidelines of the International Working Group (IWG) reported by Cheson et al. (2007). The data used for the primary statistical analyses will be derived from a central independent review of the radiological + clinical disease assessments. A charter outlining the central imaging plus clinical assessment will be prepared.

Approximately 80 patients with R-R DLBCL who meet the inclusion criteria and have none of the exclusion criteria will be enrolled in the study. This study will be conducted under a United States (US) Food and Drug Administration (FDA) Investigational New Drug (IND) application.

5.2 Schedule of assessments

For a detailed schedule of assessments, please refer to the Protocol Section 7.

5.3 Determination of sample size

Approximately 80 patients with R-R DLBCL who meet all of the inclusion criteria and have none of the exclusion criteria will be enrolled into the study. The study will be performed with an interim stop for the evaluation of the safety of the LEN dosage. No adjustment of sample size or adaptation of efficacy evaluations will be made at this point. As the primary purpose of this study is to evaluate the clinical efficacy of 25 mg daily oral LEN combined with 12 mg/kg MOR00208 administered by IV infusion in patients with R-R DLBCL, no formal statistical hypothesis testing will be performed.

**STATISTICAL ANALYSIS PLAN**MorphoSys AG
MOR208C203

For the determination of a suitable sample size, it is assumed that the combination treatment could improve the ORR of LEN from a value of 20% (under monotherapy) to 35% (under combination therapy). Applying an exact binomial test with a two-sided significance level of 5% and a power of 85% the estimated sample size is 73 patients (calculation performed by nQuery Advisor® 7.0). According to this scenario an observed ORR of 32% would lead to the conclusion that the outcome is statistically superior to outcomes observed previously for the monotherapy. Assuming a drop-out rate of 10%, a total sample size of about 80 patients is estimated.

The sample size determination has been conducted using various possible monotherapy and combination effect ORR rates and various power assumptions. Literature evaluation of study results concerning the ORR rates of LEN or comparable products (as mono- or combination therapy) as well as study results for MOR00208 ongoing studies were used to justify assumptions on response rates (Witzig et al., 2011; Wang et al., 2013).

5.4 Timing of analyses**5.4.1 Safety run-in analysis**

A Safety Review Panel consisting of the sponsor, a representative of the participating investigators and two independent expert clinical haematologists will perform a clinical safety review after the first six patients have been accrued based on the number and type of AEs occurring during the first cycle and on laboratory values (biochemistry and haematology). A total of six patients will be evaluated. A LEN dose will be considered tolerated or in need of reduction after discussion of these data between the sponsor's Clinical Program Leader (or designee), the sponsor's Drug Safety Officer (or designee), a representative of the participating investigators and two expert clinical haematologists who are not participating in the study. The second part of the study will only be opened for enrolment by the sponsor following the outcome of this discussion.

5.4.2 Primary analysis

The primary analysis will be conducted earliest after all patients have undergone at least one post-baseline response assessment (for those patients who did not discontinue before due to reasons such as death, adverse event, informed consent withdrawal etc.). The sponsor will decide when to perform the primary analysis (approximately 12 months after the last patient has been enrolled). All results of the primary analysis will be made available to MorphoSys AG prior to completion of the final CSR.

5.4.3 Final analysis

The final analysis will be performed when all patients have performed their End of Treatment visit. The analyses will be conducted after database lock. All study results will be made available to MorphoSys AG prior to completion of the final CSR.

MorphoSys may perform further exploratory analyses to investigate correlations between different biomarker and response variables. Any post-hoc, exploratory analyses completed to support planned study analyses, which were not identified in this SAP, will be documented and reported in appendices to the CSR, but will not necessitate an update of the final SAP. Any results from these unplanned analyses (post-hoc) will also be clearly identified in the text of the CSR.

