5.3 Study Duration

5.3.1 Study Conduct

The study duration per patient will be at least 5 years including periods of screening (up to 28 days from signature of the Informed Consent Form (ICF), the treatment period (maximum 12 cycles for LEN + MOR00208 followed by MOR00208 monotherapy thereafter) and the survival follow-up phase. MOR00208 can be administered until disease progression as described in [Section 5.1.2](#).

The survival follow-up phase begins with the End of Treatment (EOT) Visit ([Section 7.2.2](#)). Patients will have an on-site safety evaluation visit 30-days after last administration of study treatment (LEN + MOR208 combination or either LEN or MOR208 if one of these two drugs was discontinued earlier) (30-Day Follow-up Visit). All patients discontinued for any reason other than withdrawal of consent, or death, will be contacted every 90 days by phone from the date of the 30-Day (Safety) Follow-up Visit until end of study, or until withdrawal of consent, or death, whichever comes first.

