5.3.2 End of Study

The end of the study is defined as the date of the last visit of the last patient completing 5 years study duration. If any patient is on treatment at the end of the study and MOR00208 is not yet commercially available, patients will be switched to alternative methods of supply with MOR00208, upon assessment of a clinical benefit of continued treatment by the investigator, and in accordance with the local regulatory guidance. Upon study closure, MorphoSys will notify the applicable regulatory agencies in accordance with local requirements.

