⁹After 30-Day Follow-up Visit, a call will be made to the patient (or the patient's family) every 90 days for at least 5 years from Cycle 1 Day 1 to inquire about the patient's status, second primary malignancy (SPM) and information on any antineoplastic therapies utilised since discontinuation of study treatment.

¹⁰After disease progression has been recorded, only anticancer treatments and, in case of an AE, other relevant concomitant medications (at the discretion of the investigator) should be entered. Before and up to the End of Treatment Visit, the complete concomitant medication needs to be recorded.

¹¹A limited PE (L) will be performed on Day 1 of each Cycle, every 12 weeks \pm 2 days from the previous PE.

¹²Anti-MOR00208 antibody sample and MOR00208 PK sample (pre-dose only) will be taken in odd numbered additional treatment cycles only (i.e. treatment Cycles 13, 15, 17, 19, 21, 23). No samples to be collected after Cycle 23.

¹³Disease assessment by CT/MRI of neck, chest, abdomen & pelvis with iv contrast during additional treatment phase; Cycles 13-24: approximately every 3 months \pm 2 days from the previous scan. First assessment during this phase can be done directly 3 months after Cycle 12 D28 PET/CT assessment. Thus, this assessment is not needed at Cycle 13 Day 1, and an interval longer than \sim 3 months is acceptable for Cycle 16 Day 1 assessment; Cycle 25 onwards: approximately once every year \pm 2 weeks from the previous scan. Images will have to be transferred to the central imaging laboratory.

¹⁴In case the patient is withdrawn from treatment before the end of Cycle 12 for reasons other than progression of disease. PET/CT is only required at the EOT visit if it was not performed in the cycle before the end of treatment visit.

¹⁵Bone marrow assessment during additional treatment phase (Cycles 13 to 24) approximately every 3 months \pm 2 weeks from the previous assessment; to be performed to confirm a CR only in those patients who had known bone marrow involvement prior to dosing. Refer to [Section 7.2.14.2](#) for further details.

¹⁶HBV-DNA to be measured and re-measured only if anti-HBc was positive at screening. If HBV-DNA is positive at screening, or during treatment, please see [Section 7.2.13.2](#).

¹⁷Not applicable for patients who continue receiving MOR208 despite disease progression.

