7.2.5 Survival Follow-up

After Safety Follow-up Visit, a phone call will be made to the patient (or the patient's family) every 90 days (+ 2 weeks) for to cover a duration of up to 5 years from Cycle 1 Day 1 to inquire about the patient's status, second primary malignancy (SPM) and information on any antineoplastic therapies utilised since discontinuation of study treatment. For patients who are lost to follow-up, at least three attempts of contact by the site should be made and documented in the source data.

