7.4 Data included in the analysis and cut-off date

All the analyses mentioned in Sections 8 to 16 will be performed using data collected in the database up to the data cut-off date. A cut-off date will be defined for each of these analyses and will be specified in the outputs.

Of all the termination dates of the patients included in the final analysis, the last termination visit date will be defined as the cut-off date and will be specified in the outputs.

Analyses will be based on the data collected for patients who did not fail screening, and for all patients treated prior to or on the cut-off date.

Any data collected beyond the cut-off date will not be included in the analysis. Only data with an assessment date or event start date (e.g. vital sign assessment date or start date of an adverse event) prior to or on the cut-off date will be included in the analysis. For example, if the cut-off date is 15JUN2017 then an AE starting on 13JUN2017 will be reported, whereas an AE with start date on 17JUN2017 will not be reported.

All events with an event start date either before or on the cut-off date and an event end date after the cut-off date will be reported as "continuing at the cut-off date". The same rule will be applied to events starting either before or on the cut-off date and not having a documented end date. This approach applies, in particular, to adverse event and concomitant medication reports. For these events, the end date will not be imputed and therefore will appear as missing in listings.

If it is required to impute an end date to be able to perform a specific analysis (e.g. end date after the cut-off date) the cut-off date needs to be imputed as an end date. The imputed date will be displayed and flagged in the listings.

Any data collected beyond a patient's withdrawal of consent will not be included in the analysis; except for SAEs and the date of death provided confirmed by a public registry and patient status entered after the date of withdrawal of consent e.g. end of treatment, end of post-treatment follow-up.

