7.5 Specifications and Analysis Database

Based on dataset in SDTM format provided by [REDACTED]'s Clinical Data Services group analysis datasets adhering to CDISC ADaM standard will be generated with SAS[®] software, version 9.4 or above, based on the soft lock of data for the main analysis or hard lock study database for the full final statistical analysis (after all the patients discontinue the study) and according to agreed Analysis Dataset Specifications (ADS).

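### SAP 5.4.3 ties the final analysis to the last End of Treatment visit, which conflicts with SAP 7.5 and the protocol's 5-year end of study; the final cut-off in SAP 7.4 rests on an undefined visit

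*SAP*

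**What the plan says.** The SAP describes the final analysis in three places.

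- Section 5.4.3 gives the timing: "The final analysis will be performed when all patients have performed their End of Treatment visit". It adds that the analyses follow database lock.
- Section 7.5 describes the "hard lock study database for the full final statistical analysis (after all the patients discontinue the study").
- Section 7.4 fixes the data cut-off: "the last termination visit date will be defined as the cut-off date". The SAP does not define a termination visit. The same section excludes data collected after the cut-off, and section 6.10 caps the last-contact date, used to censor OS and TTNT, at the cut-off.

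The protocol sets a different end point. In 5.3.1, "The survival follow-up phase begins with the End of Treatment (EOT) Visit" and "The study duration per patient will be at least 5 years including periods of screening". In 5.3.2, "The end of the study is defined as the date of the last visit of the last patient completing 5 years study duration". Survival calls are made by phone every 90 days. Section 7.2.5 runs them "for to cover a duration of up to 5 years from Cycle 1 Day 1", while the footnote to the visit schedule has "every 90 days for at least 5 years from Cycle 1 Day 1".

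**The concern.** The End of Treatment visit is where survival follow-up starts, so it is an odd point at which to close an analysis that includes survival. Taken literally, 5.4.3 guarantees no follow-up after treatment: the last patient to stop could contribute none. How mature the final OS is would then depend on when that one patient comes off drug, not on a planned duration.

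The analyses exposed are those that use data after treatment ends:

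- OS, with landmarks at 36 and 48 months (SAP 10.4.4) and 48-month forest plots (Addendum 8.0).
- TTNT (SAP 10.6.2), whose event is the next therapy or death.
- OS counted from the end of both drugs (SAP 20.4.1 and 21.1).

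An End of Treatment trigger does suit PFS, because SAP 20.9 notes that PFS follow-up stops with treatment.

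**Working it through.** The plan gives no event target, power or minimum follow-up for OS, so there is no figure to reproduce. The check is a comparison of the texts, followed by an illustration.

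**Texts side by side**

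| Source | What closes the final analysis or the study |
|---|---|
| SAP 5.4.3 | All patients have had the End of Treatment visit |
| SAP 7.5 | All patients have discontinued the study |
| SAP 7.4 (cut-off only) | Last termination visit, undefined |
| Protocol 5.3.2 | Last patient completes 5 years |

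A patient in survival calls has passed the End of Treatment visit but has not discontinued the study. The first two rows therefore differ for every such patient. Under the last row, every patient alive and in contact has 60 months of follow-up, which covers the 48-month landmark.

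**Illustration 1: precision of 48-month OS**

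The planned size of about 80 is from SAP 5.3. The rest is assumed, because the documents do not give it: uniform accrual over 20 months, exponential OS with a 24-month median, and a last End of Treatment visit 36 months after last enrolment. Potential follow-up is then uniform from 36 to 56 months.

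- S(48) = 0.5^(48/24) = 0.25.
- Share with at least 48 months' potential follow-up = (56 − 48)/20 = 0.40.
- At risk at 48 months: 80 × 0.40 × 0.25 = 8, against 80 × 0.25 = 20 with 60 months for all.
- Deaths observed: about 59, against 80 × (1 − 0.5^(60/24)) = 66.
- Large-sample Greenwood variance = S(48)²/n × ∫ λ du / (S(u)G(u)) from 0 to 48, where λ = ln 2/24 and G(u) is the share with potential follow-up beyond u.
  - Early cut-off: the integral is 1.828 (0 to 36) + 1.836 (36 to 48) = 3.664. SE = √(0.0625 × 3.664/80) = 0.0535, or 5.4 points.
  - 60 months for all: the integral is 1/0.25 − 1 = 3. SE = √(0.0625 × 3/80) = 0.0484, or 4.8 points.

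With a 36-month median the same formula gives 6.0 against 5.5 points. Simulation of the 36-month cut-off agrees: 5.3 against 4.8 points, and 5.9 against 5.4. The mean 48-month estimate hardly moves (25.1% against 25.2%; 39.7% against 39.6%).

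A last End of Treatment visit at 30 months is harsher. With a 24-month median, 80 × 0.10 × 0.25 = 2 patients are at risk at 48 months. The SE is 6.2 points by simulation and 6.8 by the formula, which is rough with so few at risk.

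**Illustration 2: how far apart the two dates fall**

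A second simulation (80 patients, 2,000 runs per scenario) assumed accrual over 12 or 24 months, median time on treatment of 6 or 12 months, and median survival of 12 months after treatment.

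| Still on drug at 60 months | Mean gap, last End of Treatment to study end | Mean deaths missed |
|---|---|---|
| 0% | 3.8 to 26.7 months | 0.7 to 10.0 of about 69 to 75 |
| 10% to 20% | 0.5 to 2.6 months | about 0.1 or fewer |

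The loss therefore turns on whether anyone stays on treatment long term. One such patient puts the last End of Treatment visit at that patient's entry plus about 60 months, so the gap cannot exceed the time from that entry to the last enrolment.

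**The case against.** The strongest reply is that SAP 7.5 already settles the matter. Section 5.4.3 makes the analysis follow database lock, and 7.5 says that the full final analysis uses the hard lock taken after all patients have discontinued the study. On that reading the last End of Treatment visit is only an earliest condition. This is a fair reading and it limits the point. It does not remove the point, because 5.4.3 does not present itself as a minimum, and neither section names the 5-year end of study.

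The early-stop case also needs every patient to be off drug. MOR00208 has no maximum duration and may continue after progression. If each of 80 patients independently had a 5% chance (assumed) of being on drug at 5 years, the chance that none is would be 0.95^80 = 1.7%; at 2% it is 0.98^80 = 20%.

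A reader might infer more than the documents support:

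- *That the database will be locked with survivors still under follow-up.* SAP 7.5 points the other way; this follows only if 5.4.3 overrides it.
- *That the SAP has three competing triggers.* Section 7.4 gives a cut-off, and its termination visit may mean study termination, in agreement with 7.5.
- *That the last End of Treatment visit can never fall after study end.* Protocol 5.3.2 foresees patients still on drug then and does not say when, or whether, they have that visit.
- *That OS would be biased.* An early cut-off is administrative censoring.
- *That late second malignancies drop out of the AE summaries for this reason.* Under the SAP's TEAE definition, events more than 30 days after the last dose count only if drug-related, whatever the cut-off.

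The SAP was written to protocol version 6.0 and the protocol supplied is version 8.0, so the earlier end-of-study wording cannot be checked. The addenda as supplied leave 5.4.3 unchanged.

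**Conclusion.** The inconsistency is real and minor. SAP 5.4.3 conflicts with SAP 7.5 and with Protocol 5.3.1 and 5.3.2, and the SAP 7.4 cut-off hangs on an undefined visit. Data after treatment would be lost only if 5.4.3 governed and all patients stopped MOR00208 well before 5 years. The cost would then be precision and maturity of the final OS, TTNT and post-L-MIND survival: about half a percentage point on the SE of 48-month OS in the 36-month illustration, and more if the last patient stops earlier. All such figures rest on assumed accrual, survival and last End of Treatment timing. OS is descriptive with no hypothesis test, and the primary ORR is unaffected.

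**What to change.** - **SAP 5.4.3:** perform the final analysis after the end of study as defined in Protocol 5.3.2, that is, when the last patient completes 5 years, or earlier if all patients have died, withdrawn or been lost to follow-up.
- **SAP 7.4:** define the final cut-off as the date of the last study or survival follow-up contact, in place of the termination visit.
- **SAP 7.5:** keep the hard-lock wording consistent with both.

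The change is to SAP wording only and needs no new data. Its cost is that the final report may come later if all patients stop treatment early.
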